### **12.3 Confidentiality Regarding Study Subjects**

The Principal Investigator must assure that the privacy of the subjects, including their personal identity and all personal medical information, will be maintained at all times. In eCRFs and other documents submitted to the Sponsor, subjects will not be identified by their names, but by an identification code (e.g., subject or screen number).

The site monitor, properly authorized persons on behalf of the Sponsor's quality assurance unit, or competent authorities may scrutinize personal medical information for the purpose of verifying data recorded on the eCRF. Personal medical information will always be treated as confidential, according to local privacy regulations.

## **13 STUDY MANAGEMENT & ADMINISTRATION**

### **13.1 Protocol Amendments**

No amendments to the protocol will be implemented without the prior written consent of the Sponsor. Should an amendment be necessary, the reviewing IRB and FDA may require review and approval prior to its implementation.

### **13.2 Monitoring and Quality Assurance**

#### **13.2.1 Information to Study Personnel**

The Principal Investigator, [REDACTED] is responsible for ensuring that all study personnel are qualified for their designated roles and for providing information about the study to all staff members involved in the study or in any element of subject management, both before starting the practical performance of the study and during the course of the study (e.g., when new staff become involved).

The [REDACTED] site monitor is responsible for initiating the site, conducting interim monitoring visits, ensuring site compliance with the protocol and closing out the site at the end of the study. Additional information available during the study should be given as agreed upon, either by the Principal Investigator or the site monitor, and always when new staff members become involved in the study.

#### **13.2.2 Study Monitoring**

[REDACTED] clinical monitors will conduct approximately two interim monitoring visits at each study site in order to ensure compliance to the protocol, applicable regulations, and ICH-GCP, and to ensure safety of the subjects and maintenance of adequate and accurate clinical records.

Monitoring functions will be performed in compliance with recognized GCP and as per the study specific Monitoring Plan. The Principal Investigator agrees to allow the site monitors, and other authorized Sponsor personnel, access to the clinical supplies, the investigational agent dispensing and storage area, subject medical records, laboratory data, and other source documentation of the study subjects. Approximately two on-site interim monitoring visits will be conducted at each site, and a dedicated close-out visit will also be conducted at each site.

Source Document worksheets for all subjects and eCRFs will be reviewed in detail by the site monitor to ensure data integrity. If errors or omissions are found in the course of a data audit, or if clarification of data is required, the eCRFs and/or worksheets in question will be corrected by the study coordinator and confirmed/signed for by the TI, as appropriate. Data clarification or query forms may be generated for omissions or clarifications, to be completed and returned to the site monitor.

The dates of monitoring visits will be recorded by the site monitor in a sign-in log to be kept at the site. The Sponsor expects that, during monitoring visits, the study coordinator and Principal Investigator will be available, the source documentation will be available, and a suitable environment will be provided for review of study-related documents.

The TI and assisting staff must agree to cooperate with the site monitor to resolve any problems, errors, or possible misunderstandings concerning any data discrepancies detected in the course of these monitoring visits.

As part of the supervision of the study progress other Sponsor personnel may accompany the site monitor on visits to the study site.

### **13.2.3 Audit and Inspection**

According to ICH Guidelines on GCP, the Sponsor (or its designate) may audit the investigational site to compare raw data, source data, and associated records with the interim (if applicable) or final report of the study to assure that data have been accurately reported.

The Principal Investigator must accept that regulatory authorities may conduct an inspection to verify compliance of the study with GCP. The Principal Investigator should notify the Sponsor and [REDACTED] no later than 24 hours upon notification of being audited by the FDA or IRB.

### **13.3 Protocol Deviations**

A protocol deviation is any noncompliance with the clinical study protocol, GCP, or Manual of Procedures requirements. The noncompliance may be either on the part of the subject, the Principal Investigator, or the study site staff. As a result of deviations, corrective actions are to be developed by the site and implemented promptly.

It is the responsibility of the site to use continuous vigilance to identify and promptly report deviations to [REDACTED]

All deviations from the protocol must be addressed in study subject source documents. A completed copy of the [REDACTED] must be maintained in the regulatory file, as well as in the subject's source document. Protocol deviations must be sent to the IRB per its guidelines.

The protocol must be rigorously adhered to; however, exceptions will be made in emergency situations when the protection, safety, and well-being of the subject requires immediate intervention based on the judgment of an Investigator.

A subject identification code list will be maintained in order to allow unambiguous identification of each subject included in the study. This list should contain the subject's full name, date of birth, dates of participation and identification number as per local regulations.

The Principal Investigator must agree to supply all details to Sponsor auditor(s) and/or regulatory authorities, ensuring the data is held confidentially at the site after completion of the study. A note will be made in the hospital or clinical medical records, if appropriate, that the subject is participating in a clinical study.

The eCRF and subjects' medical records will be reviewed by [REDACTED] representatives from TEOXANE SA, the IRB, and/or the FDA to the extent permitted by regulations.

#### **14.2 Case Report Form**

In this study the case report form will be an eCRF. The study coordinator must complete the eCRF for each subject within a timely manner of the visit occurring.

The site monitor will review the completed eCRF for accuracy, completeness and consistency with source documentation (i.e., medical records, source document worksheets, etc.). The site monitor will submit requests for correction/clarification of data (e.g., queries) to the study coordinator when inconsistencies are identified during monitoring and source data verification or during the edit check process.

All corrections and alterations of eCRF data must be made by the study coordinator in a timely manner and according to the instructions provided. Completed eCRFs for each visit (i.e., those reviewed by [REDACTED] and with no remaining queries) should then be reviewed and electronically signed by the TI. In order to review and electronically sign the eCRF, the TI will each have his/her own login that will allow them to view only the data that they have generated.

A full audit trail detailing corrections and alterations made to the eCRF will be maintained.

Upon study completion, a hardcopy of the eCRF for each subject will be provided to the site.

#### **14.3 Archiving of Study Documentation**

Essential documents are any records that demonstrate the compliance of the subject, Investigators, Sponsor, and site monitor with the study protocol, with standards of GCP, and with all applicable regulatory requirements. Essential documents (including but not limited to study-related correspondence (including emails), subject records, subject privacy documentation, records of the distribution and use of study devices, and copies of eCRFs) should be retained and available for audit by the Sponsor's auditor and regulatory authorities until at least 2 years after the latest among the following scenarios: completion or termination of the study, the last approval of a marketing application, no pending or contemplated marketing applications, or formal discontinuation of clinical development of RHA® 4 [REDACTED] with [REDACTED] or RHA® 4 with lidocaine. These documents should be retained for a longer period, however, if mandated by the applicable regulatory requirements, by conditions imposed by the IRB, or by an agreement with the Sponsor. It is the responsibility of the Sponsor to inform the Principal Investigator when these documents no longer need to be retained.

The Sponsor must be notified in writing if the Principal Investigator chooses to store the records at a different physical address than the site address or if the Principal Investigator wishes to relinquish ownership of the data so that mutually agreed-upon arrangements can be made for transfer of ownership to a suitably qualified, responsible person.

## **15 FINANCING AND INSURANCE**

A separate financial agreement (Clinical Study Agreement) will be made between the Sponsor and the Principal Investigator at each site.

The study is covered under a TEOXANE SA liability insurance policy. The certificate of insurance will be provided upon request.

## 16 REPORTING AND PUBLICATION OF RESULTS

TEOXANE SA, as the Sponsor, has a proprietary interest in this study. Authorship and manuscript composition will reflect joint cooperation among multiple Principal Investigators and sites and TEOXANE SA personnel. Authorship will be established prior to the writing of the manuscript. As this study involves multiple sites, no individual publications will be allowed prior to completion of the final report of the multicenter study except as agreed with TEOXANE SA.

All information, including but not limited to information regarding RHA® 4 [REDACTED] with [REDACTED], RHA® 4 with lidocaine, or the Sponsor's operations supplied by the Sponsor to the Principal Investigator and not previously published, along with any data generated as a result of this study are considered confidential and remain the sole property of the Sponsor. The Principal Investigator agrees to maintain this information in confidence, and will use the information only to perform the study.

The Sponsor or its designee is responsible for preparing a clinical study report.

The Sponsor or its designee is responsible for publicly registering this study on <http://www.clinicaltrials.gov/> prior to initiating enrolment.

[REDACTED]

[REDACTED]

[REDACTED]

[REDACTED]

[REDACTED]

[REDACTED]

[REDACTED]

[REDACTED]

[REDACTED]	[REDACTED]
[REDACTED]	[REDACTED]
[REDACTED]	[REDACTED]
[REDACTED]	[REDACTED]
[REDACTED]	[REDACTED]
[REDACTED]	[REDACTED]
[REDACTED]	[REDACTED]

APPENDIX B: STATISTICAL TABLES	

1. INTRODUCTION

This statistical analysis plan (SAP) gives a comprehensive and detailed description of statistical techniques to be used for study **Comprehensive** The purpose of this SAP is to ensure the credibility of the study findings by pre-specifying the statistical approaches for the analysis of study data prior to database lock. This SAP provides additional details concerning the statistical analyses outlined in the protocol. Whenever differences exist in descriptions or explanations provided in the protocol and SAP, the SAP prevails.

1.1 Background

Hyaluronic acid (HA) is a long-chain, repeated dimer, N-acetyl glucosamine and D-glucuronic acid polymer and is a major component of the extracellular matrix. HA is widely present in all animal species and does not differ from one species to another. Due to this extended compatibility, non-human HA can be used in humans without unacceptable adverse effects. Due to its natural viscoelastic and hydrogel properties, HA is widely used as matrix in tissue regeneration and particularly in dermal defect reconstruction.

RHA[®] 4 and RHA[®] 4- dermal fillers are devices containing colorless, biodegradable, sterile, biocompatible, crosslinked HA of non-animal origin (i.e., bacterial fermentation using *Streptococcus zooepidemicus*). Crosslinking is performed using 1,4-butanediol diglycidyl ether (BDDE) to form a gel. RHA[®] 4 product contains 0.3% w/w of lidocaine hydrochloride, and RHA[®] 4- contains 0.3% w/w of lidocaine and contains are drug substances widely used for their anesthetic properties (i.e., they block the origin and transmission of nervous influx at the point of injection by stabilizing the neuronal membrane).

1.2 Rationale for Study

1.3 Hypothesis

The anesthetic effect of RHA[®] 4- with mepivacaine will be non-inferior to RHA[®] 4 with lidocaine in terms of injection site pain felt by the subject during injection assessed immediately after injection of each side using a 100 mm Visual Analog Scale (VAS).

1.4 Primary Objective

The study objective is to demonstrate the non-inferiority of RHA[®] 4- with versus the control (RHA[®] 4 with lidocaine) in terms of reducing pain during device injection into the NLFs. Injection pain during injection will be based on the 100 mm Visual Analog Scale (VAS), as assessed by subjects immediately after injection of each side.

2.2 Study Design Rationale

2.2.1 Study Population

Maximum 30 subjects will be enrolled and receive study treatment. The study population includes female and male subjects who are ≥ 22 years old.

See Section Erreur !

Source du renvoi introuvable. for a full description of the inclusion and exclusion criteria.

3. TREATMENT ALLOCATION, RANDOMIZATION AND BLINDING

Upon qualifying for treatment, subjects will be randomized for the side of the face and the order of injection of study devices (i.e., left or right / 1st or 2nd order).

Subjects will be considered "enrolled" at the time of consent, and will be considered "enrolled and randomized" at the time of randomization. The required sample size is based on "enrolled and randomized" subjects. If an enrolled subject withdraws from the study prior to being randomized, he/she may be replaced.

This is a double-blinded study in which subjects and TIs will be blinded to treatment allocation.

4. DEVICE APPLICATION

4.1 Injection of Study Devices

At Visit 1, each enrolled and randomized subject will receive injections of RHA[®] 4- with into the NLF of the left or right side of the face, and injections of the control device (i.e., RHA[®] 4 with lidocaine) into the contralateral NLF, to optimal correction.

4.1.2 Injection Sequence

Upon qualifying for treatment, subjects will be randomized for the side of face and the order of injection (i.e., left or right / 1st or 2nd order).

5. STUDY EVALUATIONS

5.2 Safety

Safety will be evaluated through a 30-day patient Common Treatment Response (CTR) diary that captures post-injection signs/symptoms and AE reporting based on phone follow-ups and clinic visits. Safety assessments will also include visual assessment tests.

5.2.1 30-Day Patient Common Treatment Response Diary

The subject will receive a diary booklet and instructions for recording his/her observations of the CTRs of the study treatments for the first 30 days after treatment.

The subject diary will capture the following CTRs that typically occur following the injection of a dermal filler; specifically, redness, pain, tenderness, firmness, swelling, lumps/bumps, bruising, itching, discoloration, and "other". Subjects will record the presence and the severity of each observed sign/symptom as: none, mild, moderate, or severe.

5.2.3 Adverse Events

The Investigator will assess AEs and record details of seriousness, severity, duration, and action taken with the study device, and relationship to the study device. AEs will be reported from the time of consent until the final visit, or to 30 days following the last treatment.

lidocaine.

6. STATISTICAL METHODS

6.1 Primary Endpoint

The primary endpoint will be the injection site pain during injection into one NLF assessed by the subject immediately following injection with RHA[®] 4- with **during** compared to the injection site pain felt during injection into the contralateral NLF assessed immediately following injection with RHA[®] 4 with lidocaine.

The effectiveness of RHA[®] 4- with will be demonstrated if the injection site pain during injection assessed by the subject immediately following injection with RHA[®] 4- with is statistically non-inferior to the injection site pain felt during injection of the contralateral NLF assessed by the subject immediately following injection with RHA[®] 4 with

The primary endpoint will use the PP population, a paired design and will be analyzed using hypothesis test.

For achieving non-inferiority, the observed p value must be ≤ 0.05 , taking account of the non-inferiority margin (i.e., 10mm difference in Pain VAS between the two treatment groups).

In case of non-inferiority, for achieving superiority of RHA[®] 4- with with over RHA[®] 4 with lidocaine in terms of reducing pain, the observed p value must be ≤ 0.05 .

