6.3 Safety Endpoints

6.4 Analysis Populations

Three subject analysis populations are defined: Intent-to-Treat (ITT) Population, Per Protocol (PP) Population, and Safety (SAFT) Population. All analysis populations will be defined and determined prior to database closure and unblinding for the final analysis.

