6.7 Effectiveness Analysis

6.7.1 Primary Endpoint

Effectiveness of RHA[®]4- with versus control will first be analyzed in a noninferiority statistical model using the pain felt by the subject during injection. If non-inferiority is achieved, pain felt by the subject during injection will be tested for superiority (i.e., to confirm if RHA[®] 4- is superior to RHA[®] 4 for reducing pain).

Wilsoner signed work toot		
wilcoxon signed-rank test		

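### On the visible text of SAP 6.1, superiority is tested in the PP population; assign it to ITT, and confirm that ITT also supports the PP non-inferiority test

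*SAP*

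**What the plan says.** SAP 6.1 sets the population for the primary endpoint: "The primary endpoint will use the PP population, a paired design and will be analyzed using hypothesis test". The sentence is not limited to the non-inferiority step. The section then gives two decision rules. The first is non-inferiority at p ≤ 0.05 against a 10 mm margin on the pain VAS. The second begins "In case of non-inferiority, for achieving superiority of" and again requires p ≤ 0.05. Neither rule names a population.

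SAP 6.7.1 repeats the order of testing: "If non-inferiority is achieved, pain felt by the subject during injection will be tested for superiority". Its visible part names no population either, and nor does Protocol 11.7.1.

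SAP 6.4 lists the sets: "Three subject analysis populations are defined: Intent-to-Treat (ITT) Population, Per Protocol (PP) Population, and Safety (SAFT) Population". It also says when membership is settled: "All analysis populations will be defined and determined prior to database closure and unblinding for the final analysis". The text under 6.4.1 to 6.4.3, most of SAP 6.7.1 and Appendix A, and Protocol 11.1 to 11.5 are not in the public copy. The visible part of SAP 6.1 also appears to have gaps.

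**The concern.** The two tests call for different sets. For non-inferiority, PP is a defensible deciding set, because keeping subjects with important deviations can blur a real difference between devices. For superiority, the usual basis is the set as randomized, so that the claim does not also depend on post-randomization exclusions being unrelated to device. SAP 6.1 puts both tests under one population sentence.

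The randomized set should be nearly complete here. SAP 4.1 says "At Visit 1, each enrolled and randomized subject will receive injections of" both devices, one per side, and Protocol 9.3.1.1 has each side rated immediately after its injection. A usable pair should therefore exist for almost everyone, including subjects later excluded from PP. Protocol 10.2 says deviations do not cause automatic withdrawal, so the two sets can differ.

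The trial is small, with at most 30 subjects. SAP 3 counts the sample size in randomized subjects, and the visible text mentions replacement only before randomization: "If an enrolled subject withdraws from the study prior to being randomized, he/she may be replaced". Each PP exclusion therefore removes a pair that is not visibly replaced.

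Two things are at stake: the basis of any superiority claim, and whether a reader can see if the non-inferiority verdict turns on a few excluded subjects.

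**Working it through.** **No figure of the plan to reproduce.** The SD, power and dropout behind the 30 subjects are not visible. The check asks how much the choice of set could matter.

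**Inputs from the documents.** At most 30 pairs; margin 10 mm; p ≤ 0.05 for each test; Wilcoxon signed-rank test named in SAP 6.7.1; populations fixed before unblinding (SAP 6.4).

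**Assumptions.** Paired-difference SD 15 or 20 mm; between-subject SD 20 mm; mean pain 30 mm plus half the true difference; VAS not truncated; 1, 2 or 3 exclusions made without knowledge of device. Sidedness is not visible. I take non-inferiority as one-sided 5%, and superiority as two-sided 5%, that is 2.5% in the favourable direction.

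**Step 1: shift in the mean.** If k of 30 subjects are excluded, their mean difference is D and the PP mean is 0, the ITT mean is k × D / 30.
- k = 1, D = 20 mm: 1 × 20 / 30 = 0.67 mm.
- k = 3, D = 20 mm: 3 × 20 / 30 = 2.0 mm, or 20% of the margin.

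**Step 2: simulation.** 100,000 trials per cell, exact one-sided Wilcoxon test, d = test minus control. Non-inferiority tests d − 10; superiority tests d. ITT is all 30 pairs. PP drops k subjects at random, or those with the highest total pain, or those with the highest pain on either side.

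| Quantity | ITT | PP, k = 1 to 3 |
|---|---|---|
| Superiority error, true 0 | 2.5% | 2.3–2.5% |
| False non-inferiority, true +10 mm, random or total-pain rule | 4.7–4.8% | 4.7–5.0% |
| False non-inferiority, true +10 mm, either-side rule | 4.7–4.8% | about 5.8%, 6.8%, 7.4% |

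The either-side figures depend on the assumed between-subject SD: 5.3–6.3% at 30 mm and 6.8–11.2% at 10 mm.

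**Step 3: discordant non-inferiority verdicts at a true difference of 0.** Random rule, k = 1 / 2 / 3: 1.4 / 2.0 / 2.8% (SD 15) and 4.4 / 6.1 / 8.1% (SD 20). Over all three rules the ranges are 1.4–2.9% and 4.3–8.5%.

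**Step 4: superiority power at a true −10 mm.**

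| Who is excluded | SD | ITT | PP | ITT minus PP, points |
|---|---|---|---|---|
| 1 to 3 at random | 15 mm | 93.2% | 92.1–90.3% | +1.1 to +2.9 |
| 1 to 3 at random | 20 mm | 73.3% | 71.4–68.3% | +1.9 to +5.0 |
| 3 with no device difference on average | 15 mm | 86.7% | 90.3% | −3.6 |
| 3 with no device difference on average | 20 mm | 63.8% | 68.5% | −4.7 |

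The direction of the power effect therefore depends on who is excluded.

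**The case against.** **ITT may already have its role.** A reader might infer that the plan has no ITT analysis of the primary endpoint. The documents do not support that. ITT is a named population, and the sections that would assign its use are missing from the public copy. This objection stands. For non-inferiority the request is to confirm, and to add only if the analysis is absent.

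**SAP precedence.** The SAP introduction says "Whenever differences exist in descriptions or explanations provided in the protocol and SAP, the SAP prevails". A reader might infer that 6.1 must therefore be complete by itself. It need not be: the rule ranks the SAP over the protocol, and SAP 6.4, 6.7.1 and Appendix A are SAP text too.

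**Inflated error.** A reader might infer that PP inflates false superiority. Under exclusions blind to device it does not (step 2). In a paired t simulation at one-sided 2.5%, error reached about 7%, 13% and 21% when the 1, 2 or 3 subjects least favourable to the test device were dropped. That requires selection by device-specific result, whereas the SAP fixes membership before unblinding. The 5.8–7.4% false non-inferiority likewise needs an assumed highest-pain rule that no visible text suggests. The fix would not lower it, because PP still decides that test.

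**Low stakes.** The hypothesis and objective are non-inferiority only, and superiority is a conditional follow-on. The ratings come right after injection at one visit, so the two sets may nearly coincide. The Protocol Synopsis says the sample size was increased to 30, and since the reason is not visible, an allowance for exclusions cannot be ruled out. All of this stands and limits the severity.

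What remains is the visible wording: an unrestricted PP sentence followed by a superiority rule with no other population.

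**Conclusion.** The point holds, at low severity. On the visible text of SAP 6.1, superiority is tested in PP. ITT is the better basis because the claim then rests on randomization and not also on exclusions made afterwards. That the plan lacks ITT support for non-inferiority is not established.

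The expected numerical effect is small. Superiority error is about 2.3–2.5% in either set. At a true difference of 0, the two non-inferiority verdicts differ in about 1–3% of trials (SD 15 mm) or 4–8% (SD 20 mm). These figures rest on assumed SDs and on 1 to 3 blind exclusions out of 30; the PP and ITT definitions are not visible. The gain is mainly in the standing of a superiority claim and in showing whether the non-inferiority verdict depends on excluded subjects.

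**What to change.** In SAP 6.1 and 6.7.1, before unblinding:

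1. State that superiority, tested only after non-inferiority is shown, uses the ITT (randomized) population.
2. Keep PP as the deciding set for the 10 mm non-inferiority test.
3. Confirm that the same non-inferiority test in ITT is a prespecified supportive analysis, or make it one. Report both results and say in advance how a disagreement will be described.

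If the text missing from the public copy already says this, confirmation is enough.

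The cost is a few sentences and one rerun of the same test. The non-inferiority criterion and its power do not change, because PP still decides. Superiority power is the one trade-off: a modest gain if exclusions are random, and a loss of similar size if the excluded subjects show no device difference.
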